#### Biomarker of prognosis and response to ketamine treatment

There is an urgent need of a biomarker of prognosis and response to treatment in patients with MDD. Pharmacogenetic studies have been trying to use genetic variants to predict the response to specific medications in patients, but most of the studies are still underpowered and the high genetic heterogeneity of the MDD population is hindering replication of most findings (Fabbri and Serretti, 2015). Specifically, associations with genetic variants are especially complicated because they require very large sample sizes and not often look into the functionality of those variants. In this context, switching the focus to functional genetic markers, such as DNA methylation and gene expression levels, to predict a priori the response to treatment, would overcome those limitations and allow for a more accurate and dynamic measure of how the cells of a given patient will actually respond to potential medications. This approach has been proposed by a recent study showing that the ex vivo cellular response to medications can predict the clinical outcome of the treatment in vivo. Specifically, the degree to which paroxetine reduced the phosphorylation of the enzyme DNA methyltransferase (thereby reducing its activity and increasing the expression of neurotrophic genes) in peripheral blood mononuclear cells of depressed patients significantly correlated with the reduction of depressive symptoms after six weeks of treatment (Gassen & Fries et al., 2015). In other words, the failure to improve symptoms was detected after seventy two hours of ex vivo treatment in blood cells. In this sense, the study aims to observe specific expression and/or methylation

markers measured in blood cells isolated treated ex vivo with a single dose of ketamine and its correlation with the clinical response to treatment in patients with treatment-resistant depression.

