**OPTIONAL: Blood Tests:**

**Gene Expression and Methylation:** The study aims to identify alterations in gene expression and methylation markers induced by the ex vivo treatment of peripheral blood mononuclear cells from symptomatic patients with treatment-resistant depression with ketamine and assess their correlations with clinical response (as measured by the reduction in the Hamilton Depression Rating Scale - HDRS). For that end blood samples will be collected from all subjects immediately before the first administration of ketamine, and peripheral blood mononuclear cells will be isolated with Ficoll-Paque®, according to the manufacturer's instructions. Cell will then be re-suspended in RPMI and plated at  $4 \times 10^5/cm^2$ . After recovery for 6 hours, cells will be treated with ketamine or vehicle. RNA and DNA samples will be isolated from peripheral blood mononuclear cells immediately after treatment (2 hours) and interrogated by RNA-sequencing (Ion Proton, Thermo Fisher) and the Infinium MethylationEPIC kit

(Illumina), respectively, according to the manufacturer's instructions. The reduction in the HDRS scores from baseline to post treatment will then be correlated with the alterations in the markers from both analyses, and the markers that show the strongest correlations with the reduction in HDRS will be selected. Moreover, expression and methylation markers will be compared between responsive and non-responsive patients. This will lead to the identification of a 'treatment response biosignature' incorporating information from gene expression and DNA methylation that can predict the response to ketamine in patients. **BDNF:** Ketamine and metabolites levels will be measured at baseline, 40 mins, 2-4 hours and 24 hours after ketamine infusion and serum BDNF tests will be performed at baseline (before each infusion), 2-4 hours and 24 hours after each infusion. Samples will be stored at Behavioral and Biomedical Sciences Building (BBSB) for analysis. BDNF concentrations were quantitatively determined by enzyme-linked immunosorbent assay (ELISA). A trained personnel will collect up to a **total** of 10 8 cc tubes (about 5.4 tablespoons) of blood from one subject in all the visits combined. A maximum of 4 8 cc tubes of blood (2.5 tablespoons) will be drawn per day from an individual.

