### **Study Population**

We will enroll 20 patients with Treatment Resistant Depression (TRD) in this study. Participants will be male and female adults, aged 18-60 years, who meet the criteria for TRD. Participants will be recruited without regard to race, religion or ethnicity. Children will NOT be included in this research. Children younger than 18 are excluded as the incidence of TRD is relatively small in individuals less than 18 years old and because the safety and efficacy of the proposed study medication and treatment should be established in adults first, before conducting this type of treatment research in children. No other special classes of vulnerable individuals will be included. Participants will be recruited through flyers and clinic referrals in the Houston area.

We anticipate recruiting equal numbers of male and female patient subjects. Men and women of all ethnic backgrounds will be recruited to participate. It is anticipated that the subject demographic profile will closely mirror the larger population of individuals with TRD from which they are recruited. We will do so by distributing flyers in neighborhoods known to have a high minority population.

Selection Criteria for individuals:

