### **Power Analysis**

Sample size justification: For the current proposal, our power calculation is based on our prior data on ASSR (Komek K et. al 2012) after pharmacological manipulation with effect size estimate of 0.9 and is guided by a previous study which used intravenous antidepressant clomipramine in TRD patients and found decreased motor excitability (increased RMT)(Minelli A et.al 2010) with large effect size estimate of Cohen's  $d = 1.2$ . For this project proposal, even if we assume a lower effect size of  $d=0.9$ , assuming a two-sided  $\alpha < 0.05$ , a sample of  $N=15$ , randomized in a cross-over design, participants provides 95% power to detect a difference between the two groups. Our sample size of 20 subjects would be sufficient event at attrition of 20%.

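### The ketamine-response biosignature keeps the markers most correlated with HDRS change in at most 20 patients, without error control or validation, so noise alone would make it look predictive

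*Combined protocol and SAP*

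**What the plan says.** The Gene Expression and Methylation text, under the heading "OPTIONAL: Blood Tests", plans to treat blood cells ex vivo with ketamine or vehicle. RNA and DNA are then "interrogated by RNA-sequencing (Ion Proton, Thermo Fisher) and the Infinium MethylationEPIC kit". The marker changes are correlated with the reduction in HDRS, and "the markers that show the strongest correlations with the reduction in HDRS will be selected". Markers are also compared between responders and non-responders in the same patients. The stated result is a treatment-response signature "incorporating information from gene expression and DNA methylation that can predict the response to ketamine in patients".

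On numbers, the Study Population section states "We will enroll 20 patients with Treatment Resistant Depression (TRD) in this study", and the Power Analysis allows for 20% attrition. The component is labelled optional, yet its text says "blood samples will be collected from all subjects immediately before the first administration of ketamine".

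The Statistics section names Spearman correlation for associations between continuous variables. It also plans sensitivity, specificity and predictive values, but for response status between baseline and end of study, not for a marker set tested outside the patients who produced it. No multiple-testing rule, cut-off, number of markers, cross-validation, hold-out sample or replication cohort appears in either place.

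**The concern.** A rule that keeps the strongest correlations always returns something. With a genome-wide panel and 16 to 20 patients, the largest of very many chance correlations is itself large. If the same patients supply both the selection and the claim of prediction, the apparent performance reflects the search and not the biology. The stated conclusion would then be reached even if no marker were related to response to ketamine, and a reader could not tell the two situations apart.

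The protocol shows awareness of a related difficulty. Its biomarker background says of pharmacogenetic work that "associations with genetic variants are especially complicated because they require very large sample sizes", and offers functional markers as the way round it. That remark concerns variants, not this analysis. However, moving to expression and methylation does not remove the problem of screening very many candidates in very few patients.

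Two open choices add further room for selection. The post-treatment HDRS used in the correlation is not tied to 4 hours, 24 hours or 7 days, and responder status is not defined.

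**Working it through.** **The plan's own figure.** There is none for this aim. The only sample-size statement (N = 15, d = 0.9, two-sided 0.05, 95% power) concerns ASSR and motor excitability. For the record, Φ(0.9 × √15 − 1.96) = Φ(1.526) = 93.7% by the normal approximation, and the exact two-sided paired t test gives 90.0%. Nothing below depends on it.

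**Inputs.**
- n = 20 (Study Population).
- n = 20 × 0.8 = 16 (Power Analysis attrition).
- m, the number of markers, is not in the documents. It is assumed and shown as a range.

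**Step 1: largest correlation under pure noise.** For m independent null markers, the median of the largest |r| is the value c at which P(|r| < c)^m = 0.5. The two-sided tail probability for one marker is therefore p = 1 − 0.5^(1/m). Take t from the t distribution on n − 2 degrees of freedom and convert it by r = t / √(n − 2 + t²).

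Example with m = 10,000: p = 0.0000693.
- n = 20: t = 5.135, so r = 5.135 / √(18 + 26.37) = 0.77.
- n = 16: t = 5.568, so r = 5.568 / √(14 + 31.00) = 0.83.

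| Assumed m | Median largest abs(r), n = 20 | Median largest abs(r), n = 16 | Expected null markers with p < 0.05 (0.05 × m) |
|---|---|---|---|
| 1,000 | 0.69 | 0.76 | 50 |
| 10,000 | 0.77 | 0.83 | 500 |
| 100,000 | 0.83 | 0.88 | 5,000 |
| 800,000 | 0.87 | 0.91 | 40,000 |

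For scale, Bonferroni control at two-sided 0.05 with m = 10,000 would require |r| of at least 0.83 (n = 20) or 0.89 (n = 16).

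**Step 2: a signature built from noise.** The plan does not say how many markers are kept or how they are combined, so a signed sum of the top ten is used as an illustration. With pure-noise markers, m from 1,000 to 100,000, and 200 runs per setting (60 at the largest m):
- Mean correlation with outcome in the same patients is 0.93 to 0.97 (n = 20) and 0.95 to 0.98 (n = 16).
- A median split of outcome is classified with 87% to 92% accuracy.
- Mean correlation in 200 new patients is −0.001 to 0.016, which is no prediction.

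**Step 3: nested selection.** With 20,000 null markers, a top-20 average and n = 16, the in-sample correlation is 0.98. When selection is repeated inside each leave-one-out fold, the result depends on the implementation (−0.21 to +0.09 across variants, SD about 0.37 between simulated trials). It is best read as about 0.

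**Step 4: Spearman and correlated markers.** With Spearman ranking and 20,000 null markers, either independent or in blocks of 20 correlated at 0.7, the top |rho| is about 0.86 at n = 16 and 0.80 to 0.81 at n = 20. There were ten runs per setting, so these values are indicative only.

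**The case against.** The strongest objection concerns the size of the candidate set. The text first aims to find changes induced by ex vivo ketamine relative to vehicle, and elsewhere speaks of specific markers. On one fair reading, only ketamine-altered markers go forward to the HDRS correlation, and that filter does not use outcome. By the same formula, 100 candidates give a median largest |r| of 0.58 (n = 20) or 0.65 (n = 16), and 1,000 give 0.69 or 0.76. Correlation among genomic markers also lowers the effective count. This reduces the size of the illustration. It does not supply error control or validation, and the plan states no such filter as a rule.

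Other points also carry weight. The composites are illustrative. The component is optional, the study is sized on neurophysiology, the protocol speaks of piloting new approaches, and no treatment decision uses the signature. These limit how serious the point is. They do not excuse the claim, because the text says a predictive signature will follow and does not call the result exploratory.

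A marker sample below 16 is possible because the tests are optional, but no uptake rate is given and the text also speaks of sampling everyone. Finally, cross-validation in 16 to 20 patients is itself very imprecise. It prevents a false claim but will not give a sharp estimate.

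**Conclusion.** The concern holds. Followed exactly, the plan produces a signature that appears predictive whether or not any marker is related to response. Assuming 10,000 to 800,000 independent null markers, chance alone gives a median best |r| of 0.77 to 0.87 with 20 patients and 0.83 to 0.91 with 16. The conclusion survives at 1,000 markers (0.69 and 0.76). In the simulations, composites chosen from noise correlate above 0.9 with outcome in the selecting patients and about 0 elsewhere.

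The closed-form figures assume independent normal markers, Pearson correlation and an assumed marker count; the Spearman and correlated-marker checks give a similar picture. This should be corrected before the marker data are analysed. It does not touch the neurophysiological aims.

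**What to change.** Replace the selection rule with the following:

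1. Fix one HDRS time point and define response in advance.
2. Compute rank correlations for all candidate markers and control the Benjamini-Hochberg false discovery rate at 5%, separately for expression and methylation. If only ketamine-altered markers are to go forward, state that filter and apply it without reference to HDRS.
3. Build any signature with marker selection and scaling repeated inside each leave-one-out fold. Report the cross-validated performance with a permutation p-value and a statement of its imprecision.
4. Replace the claim of prediction with candidate markers for independent validation.

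Other error-rate or resampling methods would also serve. The essential parts are control of the search, no reuse of the selecting patients as evidence of prediction, and the change of wording. The cost is analysis code and text, with no extra patients, samples or visits. The reported signature will look less favourable and may be empty.

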## Assessment

The protocol consists of three components: clinical and cognitive and neurophysiological assessments.

### Clinical assessment

This evaluation will obtain family history and demographic data. Copies of any recent medical evaluations (past medical history, physical exam, etc.) will be requested from treating clinicians and health care providers. We will perform a urine drug screening (UDS) to rule out recent undisclosed use illicit substances. Demographic information is obtained through a standardized form and covers: age, race, gender, education (information both on siblings and their parents), religion, and socioeconomic status. Handedness in all participants will be confirmed with Oldfield's Edinburgh Handedness Inventory

Patients may fill out mood questionnaires rating the severity of the clinical symptoms at various time points at the discretion of the PI.

Self-report questionnaires and Clinical Assessments to assess mood, anxiety and severity of clinical symptoms:

1. **Adult (Brief Dissociative Experiences Scale [DES-B]—modified):** to monitor the dissociative side effects, Scale features: simple, easy to use, new DSM-5 self-rated scale. Frequency: After every injection
2. **Severity Measure for Generalized Anxiety Disorder—adult:** to measure the severity of anxiety. Scale features: simple, easy to use, new DSM-5 self-rated scale. Frequency: At the discretion of the PI
3. **Snaith–Hamilton Pleasure Scale:** to measure the level of anhedonia, Scale features: easy to use, used before in ketamine studies, self-rated scale. Frequency: At the discretion of the PI.
4. **SCID-I Interview:** This is the standard psychiatric research evaluation for ascertainment of psychiatric diagnosis in the context of research studies (Spitzer et al., 2007). It is a comprehensive structured interview for determining axis I diagnosis according to the DSM-IV. Frequency: Before the start of the study
5. **Clinical Global Impression Scale (CGI):** This is a clinical instrument to assess global changes in patients' status in clinical studies. We will use the CGI-BD, for use with BD patients (Guy et al., 1976).
6. **Montgomery-Åsberg Depression Rating Scale (MADRS):** this scale rates depressive symptoms, and its psychometric properties are well-established (Montgomery et al. 1979). Frequency: Before the start of the study and at 4 hours, 24 hours and 7 days after infusion. (Changed based on the PI).
7. **Young Mania Rating Scale (YMRS):** This is a well-established clinical severity rating scale for manic symptoms that has adequate inter-rater reliability and internal consistency (Young et al., 1978). Frequency: Before the start of the study and at 4 hours, 24 hours and 7 days after infusion. (Changed based on the PI).
8. **Positive and Negative Affect Schedule (PANAS):** the PANAS comprises two mood scales, one that measures positive affect (PA) and the other which measures negative affect (NA). Used as a psychometric scale, the PANAS can show relations between positive and negative affect with personality stats and traits. Ten descriptors are used for each PA scale and NA to define their meanings. Participants in the PANAS are required to respond to a 20-item test using 5-point scale that ranges from very slightly or not at all (1) to extremely (5). This scale may be administered prior to and following each infusion to assess acute changes in mood. Frequency: Before the start of the study and at 4 hours, 24 hours and 7 days after infusion. (Changed based on the PI).
9. **The World Health Organization Quality of Life (WHOQOL)-Brief :** this scale is patient-reported and measures the degree of enjoyment and satisfaction experienced by subjects in various areas of daily functioning (*Endicott*

*et al.*, 1993). Frequency: Before the start of the study and at 4 hours and 24 hours after infusion. (Changed based on the PI).

**10. Hamilton Depression Rating Scale (HDRS):** a multiple item questionnaire used to provide an indication of depression, and as a guide to evaluate recovery. Frequency: Before the start of the study and at 4 hours, 24 hours and 7 days after infusion. (Changed based on the PI).

**11. Hollingshead Socioeconomic Status:** This scale is patient-reported and indication of socioeconomic status. Frequency: At the discretion of the PI.

**12. Columbia Suicide Severity Rating Scale**

### Cognitive assessment (Optional)

Patients may complete the BAC-A is based on the Brief Assessment of Cognition in Schizophrenia (BAC-S). The BAC-S has been validated both linguistically and psychometrically in a number of psychiatric populations, including patients with schizophrenia and BD (Cuesta et al. 2011; Cuesta et al., 2011; Hill et al., 2013; Kuswanto, Sum, & Sim, 2013; Salgado et al., 2007; Segarra et al., 2011). It has been shown to be as valid and sensitive as a traditional neuropsychological assessment and takes approximately 35 minutes to administer (Keefe et al., 2004; Velligan et al., 2004). Six of the 8 subtests of the BAC-A match those found in the BAC-S. These tests are the Token Motor Task, Symbol Coding, List Learning, Digit Sequencing Task, Category Instances (Animals) and Controlled Oral Word Association Test (F and S-words), Tower of London (Keefe et al., 2004). In addition to these 6 subtests the BAC-A comprises the Emotion Inhibition Test (a modified version of the Emotional Stroop task (LaMonica, Keefe, Harvey, Gold, & Goldberg, 2010; Williams, Mathews, & MacLeod, 1996)) and the affective auditory verbal learning test (Affective interference test). The latter task is similar to the Affective Auditory Verbal Learning Test (AAVLT) (Snyder & Harrison, 1997).

Participants may complete the Effrt task (Treadway et. al 2009) which is an effort-based decision making task using E-Prime software (Psychological Software Tools). Participants may make additional bonus money from this task and it will be added to their compensation.

Subjects may also be asked to do some simple tasks which will involve looking at a computer screen display (figures, symbols, numbers, letters, words or sentences) or listening to sounds through headphones (clicks, beeps, or words). The participant is asked to respond to the stimuli by pressing a response button. Stimuli will be presented on a computer screen using E-Prime (Psychological Software Tools, Pittsburgh, PA). Dependent variables will be reaction time, response, and accuracy collected via keyboard, joystick, button box or similar device and stored on a computer. The task will involve separate trials and trials are organized in blocks so that participants will be allowed to rest in between blocks. In each session, cognitive tasks will be presented on a computer screening using E-Prime (Psychology Software Tools, Pittsburgh, PA).

### Neurophysiological assessment (Optional)

TMS -TMS stimulation will be applied to the corresponding region of the contralateral primary motor cortex and left DPFc or Broadmann Area 6 to examine the cortical excitability measures after Ketamine infusion. EEG- EEG will be acquired as participants perform an auditory task. The purpose of EEG is to study gamma band oscillations as a marker of Ketamine's early excitatory effect on cortex. TMS and EEG will take place concurrently.

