
### Auditory steady state response (ASSR) and Gamma band oscillations

Gamma band oscillations (30-80 Hz) are thought to play a critical role sensory and cognitive processing, and in the pathophysiology of a number of neuropsychiatric disorders. The auditory steady state response (ASSR) is a widely used non-invasive electroencephalography (EEG) technique to study cortical gamma oscillations in auditory cortex. The ASSR evoked power is thought to be regulated by interaction of NMDA receptor and parvalbumin (PV) gamma aminobutyric acid (GABA) inhibitory interneuron activity on sensory cortical pyramidal [50, 51]. Ketamine and NMDA antagonists dose-dependently increases ASSR power and gamma oscillations [52, 53] and causes increased cortical excitability likely by shifting excitatory/inhibitory balance at the circuit level [25, 54, 55]. Further, there has been recent initial validations of ASSR at 40 Hz frequency as a potential marker of NMDA activity [56]. Only one study looking at ASSR using MEG study reported no change in MDD patients compared to healthy subjects but significantly larger ASSR power if compared with BD patients [57]

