**Cortical Excitability-TMS procedure:** TMS-EEG will be performed at 4 hours, 24 hours and 7 days after the infusion. Patients will be seated in an armchair with elbow semi-flexed; the forearm pronated and fully relaxed. Participants will be given ear plugs for comfort and noise safety. A MagVenture MagPro X100 transcranial magnetic stimulator system with a figure-of-eight coil (diameter=70 mm for each loop) will be placed tangentially over the scalp overlying the primary motor cortex and DLPFC. The stimulator is paired with Localite neuronavigation system which allows precisely localized stimulus application and its integration also allows

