external control of the MagPro system. EMG readings may be obtained from the APB muscle. TMS stimulation will be applied to the corresponding region of the contralateral primary motor cortex. The optimal coil position will be determined by moving the coil in 1-cm increments over the motor cortical area while delivering magnetic pulses and by observing maximal contraction of the contralateral APB. The procedure may be repeated for the opposite hemisphere. The main purpose of this study is to examine the cortical excitability measures after Ketamine. Resting motor threshold (RMT) is defined as the stimulation intensity eliciting an MEP greater than 0.5 mV in 5 of 10 trials with a relaxed APB. Intra-cortical facilitation (ICF) is defined as subthreshold conditioning stimulus set at 80% of resting MT calibrated to produce an average MEP of 0.5- to 1.5-mV peak-to-peak amplitude in the contralateral APB. A suprathreshold test stimulus follows conditioning stimulus between 10-20 milliseconds (ms) (55). Conditioning stimuli may be delivered to left Dorsolateral Prefrontal Cortex (DLPFC) or Brodmann Area 6 or Motor cortex prior to the test stimulus in 1 of 3 random inter-stimulus intervals 10 ms (ICF-10), 15 ms (ICF-15), and 20 ms (ICF-20) for ICF measures. The sequence of administration will be counterbalanced to reduce order effects. For ICF, the change in test stimulus MEP amplitude of each inter-stimulus interval was expressed as a percentage of the mean unconditioned MEP amplitude (55). TMS will be applied concurrently with EEG recordings. **EEG/EMG Acquisition and Analysis** - EEG sessions will be conducted in a sound-attenuated room lit with a low-level ambient light. EEG Brain Products Brain Amp MRPlus 64 channel system is used to acquire EEG data. EEG signals are recorded with a 64 channel cap at a high sampling rate (500 Hz) from the entire scalp, with signals amplified by a shielded, MR-compatible amplifier. The software, Brain Vision Recorder, will be used to coordinate EEG recordings with EPrime. Continuous data will be filtered off-line with a .2- to 100-Hz bandpass filter with a 60-Hz ideal notch filter. ASSR Epochs are defined as -500 to 1000 ms relative to stimulus onset adjusted to a -350 to -150-ms prestimulus baseline. Ocular and ECG artifacts will be removed with ICA-based detection and correction methods (EEGLab); [59]. Data will be re-referenced to average reference. EMG data will be obtained using the Brain Amp ExG amplifier which allows for up to 8 simultaneous bipolar recordings at a 5-kHz sampling rate via the same software as EEG data. MEP epochs will be defined as -200 to 300 relative to stimulation. ICF trials will be time adjusted to align the second pulse with single pulse trials, and MEP amplitudes will be determined as the peak to be difference identified between 10 and 50 ms post-TMS pulse. Software and hardware for the analysis of EEG/EMG data, include state-of-the-art analytic and statistical packages (e.g. EEGLab, Brainstorm, Matlab, and SPSS).

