
**OPTIONAL: ASSR/EEG paradigm:** Task - Patients will wear ER-3A insert earphones (Etymotic Research, Elks Grove, IL, USA) for auditory stimuli and will be seated ~80 cm from an LCD computer monitor used to present visual stimuli. All stimuli are presented using E-Prime software (Psychological Software Tools, Pittsburgh, PA, USA). Click trains of 500-ms duration will be presented binaurally at  $65 \pm 5$  dB. The click train repetition frequencies will be 40 Hz and presented in the context of an auditory oddball paradigm to ensure participant attention to the stimuli. Standard stimuli will be click trains with individual clicks being 1-kHz carrier frequency whereas Oddball stimuli will be click trains with clicks of 2-kHz carrier frequency. During click train presentation and for 200 ms after click train cessation, the screen remained blank (black). Participants will be then prompted by the appearance of a central fixation cross to respond by button press with either their left index finger for Standard stimuli (110 trials per block) or their right index finger for Oddball stimuli (10 trials per block). Behavioral analyses will be conducted to confirm attention to task but only correct Standard trials will be submitted for EEG analyses.

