### **Protections against risk**

1. Risks related to diagnostic procedures/questionnaires: As noted above, the primary risks related to these procedures are participant discomfort and loss of confidentiality. Regarding participant discomfort, we will make clear that we ask for this sensitive information as part of the consent process. Further, while subjects may be uncomfortable reporting these issues, the risks of serious sequelae are extremely low. Regarding confidentiality, we have rigorous procedures in place to ensure confidentiality of data, including locked cabinets for confidential files, participant coding, secure computer systems, and rigorous training of personnel. Computer systems are secure and strictly monitored by University IT staff. Laboratory staffers are trained in confidentiality of participant information. No information is allowed to leave the lab or to be accessed by a computer outside of the university's secure computer system, and all data are further protected by permissions and passwords given only to necessary research personnel. No information will be published in a form in which the participant can be identified. We will also obtain a Certificate of Confidentiality for this study to provide additional protection for sensitive information.
2. Risks related to psychophysiological monitoring: As noted above, precautions are taken to make electrical hazards from equipment unlikely, including correct grounding and optical isolation of the participant. Disease hazards are minimized through disposable electrode collars and thorough cleaning processes. Mild, transient skin irritation from cleaning procedures is common (as described above), but the possibility of more serious skin irritation will be minimized by asking participants about previous allergic reactions to rubbing alcohol or exfoliants and rigorous training in correct skin cleaning procedures for research assistants.
3. Electroencephalography (EEG): The EEG is administered by trained research staff and can be stopped at any time if the subject becomes uncomfortable.
4. Transcranial Magnetic Stimulation (TMS): Earplugs are always worn to prevent any headaches or ringing in ears caused by TMS noise. In this protocol, since it will not be repetitive TMS, the risk is very rare.

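### Read literally, the neurophysiological assessment section places TMS inside the auditory task, against the rest of the protocol; and ear plugs are the only control of coil sound for the DLPFC TMS-EEG objective.

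*Combined protocol and SAP*

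**What the plan says.** Under Neurophysiological assessment (Optional), the protocol says "EEG will be acquired as participants perform an auditory task" and, shortly afterwards, "TMS and EEG will take place concurrently". No other kind of EEG is described there.

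Under Study Design and Procedure, the TMS paragraph requires the arm to be at rest ("the forearm pronated and fully relaxed") and defines the resting motor threshold (RMT) with a relaxed thumb muscle (APB). On timing it says "TMS will be applied concurrently with EEG recordings", with no mention of a task. On sound it says "Participants will be given ear plugs for comfort and noise safety". Protections against risk adds "Earplugs are always worn to prevent any headaches or ringing in ears caused by TMS noise", and Potential Risks says the same in other words.

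The ASSR paragraph, under its own optional heading and without TMS, says "Patients will wear ER-3A insert earphones". It requires an index-finger button press on each trial: left for standard stimuli, right for oddballs.

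The Summary lists EEG/ASSR and TMS-EEG with EMG as separate items. The Objectives section makes DLPFC excitability measured by TMS-EEG a main objective. The background section on ASSR says "Ketamine and NMDA antagonists dose-dependently increases ASSR power and gamma oscillations".

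**The concern.** There are two distinct problems.

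The first is a contradiction about what is recorded. Staff working from the neurophysiological assessment section would pulse the patient during the auditory task; staff working from the Summary would run two blocks. These give different data. In the first case the ASSR epochs may contain TMS pulses, and the TMS measures come from a patient doing a motor task.

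The second remains even if the blocks are separate. A TMS coil makes a sound with each pulse, so the brain's response to that sound is time-locked to the pulse. The only measure against it is ear plugs, provided for comfort and safety. No masking, no sham or click-only condition and no analysis step for auditory activity is specified; the EEG processing names only ocular and ECG artifact removal. The study is open-label with a single arm, so nothing would separate a change in the auditory component from a change in the DLPFC response.

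**Working it through.** The plan states no figure on this point, so the check sets the passages side by side.

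**1. Can TMS and the task run together as described?**

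| Feature | TMS paragraph and risk sections | ASSR paragraph |
|---|---|---|
| Ears | Ear plugs at all times | Insert earphones in the same ear canals |
| Hands | Forearm relaxed, APB relaxed | Index-finger press on every trial |
| Trials | No task mentioned | 110 standard + 10 oddball = 120 presses per block |
| EEG window | None defined for a TMS-evoked response | −500 to 1000 ms, so 1.5 s per epoch |

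The first two rows cannot both be met at once. If TMS were delivered during the task anyway, pulses could fall inside any of the up to 110 analysable standard epochs per block.

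**2. At which visits could they overlap?** From the Summary:

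| Time | TMS | EEG/ASSR |
|---|---|---|
| Baseline | TMS-EEG | not listed |
| 10 and 40 min | not listed | may be done |
| 4 h | TMS-EEG and EMG | may be done |
| 24 h | TMS-EEG and EMG | optional |
| Day 7 | TMS only | not listed |

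Overlap is therefore possible only at 4 and 24 hours.

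**3. What would overlap do to the change from baseline?** Write a TMS measure at time *t* as *m* + *K_t* + *T* × (1 if the task is running, 0 otherwise). Here *K_t* is the change after ketamine, zero at baseline, and *T* is the effect of task state, assumed equal at both visits.

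- 4 h minus baseline = *K_4* + *T*
- 24 h minus baseline = *K_24* + *T*
- Day 7 minus baseline = *K_7*

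The task effect enters both early contrasts and is absent at day 7. With no drug effect at all, a non-zero *T* would look like an early change that has gone by day 7. More patients would not remove it.

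**4. What does coil sound do when the blocks are separate?** Write the recorded TMS-evoked EEG response as *D_t* + *A_t*, the direct cortical part plus the auditory part. Change from baseline is (*D_t* − *D_0*) + (*A_t* − *A_0*). If the auditory part is the same at every session it cancels in this difference, although it still dilutes a percentage change. If it shifts between sessions, the shift is counted as DLPFC change. The documents give neither the auditory share nor its shift, so no size can be computed.

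**5. Which outcomes are exposed?** RMT and intracortical facilitation (ICF) are read from EMG of the APB, so an auditory EEG response does not enter them directly. The DLPFC conditioning procedure is also read out as an MEP. The exposed quantity is a TMS-evoked EEG response. The DLPFC objective implies one, but the EEG analysis text defines no window or amplitude for it.

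**The case against.** The strongest reply is that the contradiction is loose wording in one summary paragraph. The TMS paragraph gives *concurrently* its ordinary meaning, EEG recorded while pulses are delivered. The ASSR paragraph stands apart and mentions no TMS. The Summary lists the two separately and, on the infusion day, puts TMS-EEG after the ASSR recordings. That stands: a reader might infer that the plan definitely runs TMS during the button-press task, and the documents taken together do not support this. They do not exclude it either. The paragraph in question defines no EEG other than task EEG, both procedures are scheduled at 4 and 24 hours, and the text gives no order at 24 hours. The study-design figure was not available to me.

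A reader might also infer that hand movement spoils the resting MEPs. That would require overlapping blocks, contrary to the relaxed-muscle requirement, and the press uses the index finger whereas MEPs come from a thumb muscle. The count of 120 presses describes the task; it does not estimate MEP error.

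A third tempting inference is that ketamine is known to change the response to the coil click. The cited statement concerns ASSR power and gamma oscillations. The protocol presents this as an acute or early effect, whereas TMS-EEG after infusion starts at 4 hours. Carrying it over to the click is plausible, but the documents do not state it.

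Finally, the remedy has its own difficulty. Masking through insert earphones competes with ear plugs for the same ear canals, and masking noise is itself a sound. The first has to be settled in the wording. The second is limited by using the same level at every session, baseline included.

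**Conclusion.** The point holds in a limited form. The neurophysiological assessment section contradicts the TMS procedure, the ear-plug statements and the Summary, and the passages must be reconciled. The harm to ASSR epochs and TMS measures, and the mixing of drug effect with task state at 4 and 24 hours, arise only if the literal wording is followed.

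Independently of that, coil sound is controlled only by ear plugs in an uncontrolled before-and-after design, so any TMS-evoked EEG response used for the DLPFC objective may include an auditory component. That this component changes after ketamine is an inference. Its size cannot be derived from the documents, and any percentage would merely restate assumed inputs. RMT and ICF are not directly affected.

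The change is worth making because it is cheap and because an auditory component recorded without masking or a control condition could not be reliably separated afterwards.

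**What to change.** 1. Amend Neurophysiological assessment so that *concurrently* means only that EEG is recorded during TMS pulses. State that TMS-EEG and EMG are done at rest with no task, in a block separate from ASSR. Fix the order at each visit where both are done: ASSR first, as the Summary implies for the infusion day.
2. During TMS-EEG blocks at every session, including baseline, play continuous masking noise through the ER-3A insert earphones already listed, at a level held constant for each patient. Reconcile this with the ear-plug wording in the TMS procedure, Potential Risks and Protections against risk, so that hearing protection is maintained. The same amendment should say whether EEG is recorded at day 7, since the TMS procedure includes that visit among the TMS-EEG times and the Summary lists TMS only.

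The cost is protocol wording and a noise track on existing equipment, with no extra patients or visits. The downsides are slight discomfort from the noise, and that masking may not remove the auditory response completely. Reports of the DLPFC response should state that limit.
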